*Examining disparity driven vergence as a potential
diagnostic test for mild traumatic brain injury (mTBI)*

NCT Number NCT03529799

1) **Protocol Title**

Examining disparity driven vergence as a potential diagnostic test for mild traumatic brain injury (mTBI)

2) **IRB Review History***

None.

3) **Objectives***

Specific Aim 1 (SA1): Determine the validity and safety of disparity driven vergence testing with a portable goggle system using a pseudorandom ternary sequence of frequencies on a group of normal subjects.

Specific Aim 2 (SA2): Determine the vergence testing control values using a portable goggle system using a pseudorandom ternary sequence of frequencies on a group of normal subjects.

Specific Aim 3 (SA3): Determine the vergence testing values with a portable goggle system using a pseudorandom ternary sequence of frequencies on a group of subjects with history of mild traumatic brain injury and compare this to values in normal subjects.

4) **Background**

Vergence eye movements for focusing on objects include either convergence, the coordinated movement of both eyes towards the midline, or divergence, the coordination movement of both eyes towards the periphery. These eye movements are thought to be controlled by complex neurophysiological mechanisms that can be susceptible to damage by traumatic brain injury. Known involved areas in vergence include the oculomotor nucleus, cerebellum, and visual association cortex (Conn 2016), all of which can sustain damage during head trauma.

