feasible, we propose a pseudorandom ternary sequence approach to frequency distribution during disparity driven vergence to allow rapid analysis over a wide range of frequencies. Essentially, a pseudorandom frequency distribution can help extrapolate data to a larger frequency data set. We will also be evaluating the safety and side effect profile of using the goggles using a medical symptom questionnaire.

5) **Inclusion and Exclusion Criteria**

Inclusion:

- Aged 18 or older
- Both females and males

Exclusion:

- Central processing disorder
- Impaired vision without corrective lenses (max 20/60 uncorrected)
- Moderate to severe hearing loss (>55dB PTA, <50% word identification)
- Vestibular disorder except for patients recruited for SA3
- History of ear surgery other than myringotomy with or without tube placement
- Pregnant women
- Prisoners
- Adults unable to consent

6) **Number of Subjects**

60 subjects – 30 normal controls (no mTBI), 30 patients with mTBI.

7) **Recruitment Methods**

Normal subjects will be recruited from a pool of patients from a population who are unaffiliated or affiliated with University of Miami and meet inclusion criteria and not excluded by exclusion criteria. The faculty and students of any University of Miami School will be recruited through advertising in e-mails. Emails will be sent to staff and faculty associated with the UM Clinical Research Building (CRB) that have their emails stored in the UM Outlook server. Subjects will not be paid to participate. Students and staff will be assured that their participation will have no effect on their school performance or grades.

8) mTBI patients will be recruited by convenience from a pool of patients with history of mTBI and no prior vestibular disorders that present to the UM CRB Otology Clinic of [name] (SA3)”. The determination of their fitness for participation will be made during [name] clinical history and physical by asking about the history of the head injury and past medical history.

9) **Study Timelines**

Vestibular tests will take 15 minutes.

10) **Study Endpoints**

Each participant’s study will be completed when they have completed the vergence testing and other vestibular tests. At that point, the data will be de- identified.

11) **Procedures Involved**

The study will be conducted in 2 phases in which each phase comprises of thirty participants.

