In the first phase, thirty participants without mTBI who meet the inclusion criteria and are not excluded will be chosen to participate. Participants will sign an informed consent document and undergo 1 session of vergence testing, along with a series of vestibular tests. After this testing, the data will be de-identified and will only be labeled with sex and age of patient.

In the second phase, thirty participants with mTBI who meet inclusion criteria and are not excluded will be chosen to participate. Participants will sign an informed consent document and undergo 1 session of vergence testing, along with a series of vestibular tests. After this testing the data will be de-identified and will only be labeled with sex and age of patient.

After the session, patients will be given a medical symptom/toxicity questionnaire (MSQ) to evaluate for any side effects.and the SCAT-5 questionnaire, which will evaluate their current symptoms.

For each vestibular test and data to be obtained, see table below:

Test	Activity	Outcome OR Ordinal Value
Vergence Pursuit	Focusing on object moving forward and backwards	0 - 100
Spontaneous Nystagmus	Focusing on an object	Normal / Abnormal (Side)
Saccades ~ Horizontal Random	Focusing on objects randomly in horizontal axis	Normal / Abnormal (Side)
Saccades ~ Vertical Random	Focusing on objects randomly in vertical axis	Normal / Abnormal (Side)
Smooth Pursuit Horizontal ~ 0.1 Hz	Tracking objects in horizontal axis, at 0.1 Hz	Normal / Abnormal (Side)
Smooth Pursuit Horizontal ~0.75 Hz	Tracking objects in horizontal axis, at 0.75 Hz	Normal / Abnormal (Side)
Smooth Pursuit Vertical ~0.1 Hz	Tracking objects in vertical axis, at 0.1 Hz	Normal / Abnormal (Side)

Smooth Pursuit Vertical ~0.75Hz	Tracking objects in vertical axis, at 0.75 Hz	Normal / Abnormal (Side)
Predictive Saccades	Tracking an object moving in predictable manner	Percent (%) Error
Antisaccade	Moving eyes away from visual onset	% Error
OKN (optokinetic nystagmus) Trapezoidal	Tracking moving field	Normal / Abnormal (Side)
Visual Reaction Time	Reaction time to object	Seconds
Saccades and Reaction Time	Reaction time to off-center object	Seconds
Auditory Reaction Time	Reaction time to sound	Seconds
Self-Paced Saccade	Saccadic motion between two fixed targets	0 - 100
Pupil Reflex	Normal light reflex	0 - 100
Subjective Visual Vertical	Ability to perceive subjective tilt	0 - 100

12) **Data Storage**

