The only data to be stored will be the results of the vergence tests and vestibular testing done during the two sessions. These results will be tied together by a subject number that will also link to the sex of the patient and age of the patient. No PHI that identifies any participant will be kept. All the previously described data will be stored on the PI's computer and used for analyses purposes in room 580 of the clinical research building at the University of Miami Medical Center located at [name]. It will be password protected, and unique identifiers used for subject protection. Data will not be distributed, except in the form of peer-reviewed publication or oral presentation maintain the confidentiality of the subjects.

13) **Data Management***

Group mean data and single subject design will be utilized. In the group mean data scoring on each of the sessions will be aggregated for each of the specific aims. First session scores will be compared to second session scores using standard statistical methods with significance defined as $p < 0.05$. For the single subject design the number of subjects for each vestibular tests for each aim who have a significant difference in scores between the first and second session will be calculated and analyzed with descriptive statistics. In this way the investigators can calculate the difference between each test on the two sessions for each protocol, as it is very possible that some tests may be significantly different between the sessions and some tests will not.

Data will be stored on the PI's computer and used for analyses purposes in room 580 of the clinical research building at the University of Miami Medical Center located at [name]. It will be password protected, and unique identifiers used for subject protection. Data will not be distributed, except in the form of peer-reviewed publication or oral presentation maintain the confidentiality of the subjects. . No PHI that can identify any subjects will be kept beyond the second session of testing.

14) **Withdrawal of Subjects**

Subjects can withdraw at any time but if they withdraw their data will not be used and they will be replaced in the study by a new subject.

15) **Risks to Subjects**

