None anticipated since this is not more than minimal risk.

25) **Economic Burden to Subjects**

None anticipated.

26) **Consent Process**

Consent will be obtained by the PI, Sub-I, or study coordinator in the Ear Clinic at the University of Miami Medical Center any participants who wish to enroll in the study will be consented at the ENT clinic prior to initiating any study procedures. Informed consent will be obtained in writing via the attached documents. Participants will be taken into a private room to read the consent form and have any questions regarding the study answered by a research team member.

Waiver or Alteration of Consent Process (consent will not be obtained, required information will not be disclosed, or the research involves deception)

No Waiver being sought

Subjects who are not yet adults (infants, children, teenagers)

Not part of subject population

Cognitively Impaired Adults

Not part of subject population

Adults Unable to Consent

Not included in subject population

References

Conn PM. "Vision." *Conn's Translational Neuroscience*. San Diego: Academic Press, 2017. 399-438.

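### Section 14 discards and replaces everyone who withdraws, safety data included, so subjects who stop because of symptoms can vanish from the SA1 side-effect result

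*Combined protocol and SAP*

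**What the plan says.** The withdrawal rule is the single sentence of Section 14 (Withdrawal of Subjects). Subjects may leave at any time, but "if they withdraw their data will not be used and they will be replaced in the study by a new subject". It does not distinguish between types of data or reasons for leaving.

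Safety is a stated aim. Section 3 gives SA1 as: "Determine the validity and safety of disparity driven vergence testing with a portable goggle system", in normal subjects. Section 4 (Background) adds: "We will also be evaluating the safety and side effect profile of using the goggles using a medical symptom questionnaire". Section 11 (Procedures Involved) sets the timing: "After the session, patients will be given a medical symptom/toxicity questionnaire (MSQ) to evaluate for any side effects".

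Three other sections bear on the point:

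- Section 6 fixes the groups at "30 normal controls (no mTBI), 30 patients with mTBI".
- Section 10 says that each participant's study "will be completed when they have completed the vergence testing and other vestibular tests".
- Section 26 says that participants "will be consented at the ENT clinic prior to initiating any study procedures".

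Nothing in the document keeps safety data from withdrawn subjects, defines a safety population of everyone who started testing, or asks for the number of withdrawals and the reasons to be recorded or reported.

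**The concern.** Dropping and replacing subjects who leave may be tolerable when the aim is a set of vergence control values. It is not neutral for safety, because stopping on account of symptoms is itself a safety outcome. The rule can remove the events that SA1 sets out to detect.

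The document does not define withdrawal. Since Section 10 ties completion to finishing the vergence and vestibular tests, the natural reading is that a subject who stops earlier because of symptoms has withdrawn. Such a subject may never reach the MSQ, which follows the session. Giving the MSQ after a shortened session would not help either, because Section 14 would still bar use of the answers.

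Replacement then brings the group back to 30, so the report shows a full group and no visible gap. Because written consent precedes all procedures, the number who consented might be recovered from the forms. The reasons for stopping and the symptoms might not.

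**Working it through.** **Inputs.** From the documents: 30 normal controls, the group to which SA1 applies, kept at 30 by replacement (Sections 6 and 14). The documents give no side-effect rate, withdrawal rate or safety calculation, so there is no planned figure to reproduce. Every rate below is an assumption.

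**Notation.** *p* is the true side-effect rate, *w* the share of affected subjects who stop, and *u* the share of unaffected subjects who stop.

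**Rate seen among completers.** *c* = *p*(1−*w*) / [*p*(1−*w*) + (1−*p*)(1−*u*)].

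When only affected subjects stop (*u* = 0), this becomes *c* = *p*(1−*w*)/(1−*pw*). For *p* = 10%:

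- *w* = 25%: 0.075/0.975 = 7.7%.
- *w* = 50%: 0.05/0.95 = 5.3%.

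With *w* = 50%, a true rate of 5% reads as 0.025/0.975 = 2.6%, and a true rate of 20% reads as 0.10/0.90 = 11.1%.

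**Subjects lost from view** (*u* = 0, *p* = 10%). Expected starters for 30 completers are 30/(1−*pw*). The chance that at least one affected subject is excluded on the way to 30 completers is 1−(1−*pw*)^30. The chance that 30 completers show no side effects is (1−*c*)^30.

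| *w* | Expected starters | Expected excluded | Chance of excluding at least one | Chance of 0/30 |
|---|---|---|---|---|
| 0 | 30 | 0 | 0 | 0.90^30 = 4% |
| 25% | 30/0.975 = 30.77 | 0.8 | 1−0.975^30 = 53% | 9% |
| 50% | 30/0.95 = 31.58 | 1.6 | 1−0.95^30 = 79% | 20% |

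**If unaffected subjects stop too** (*p* = 10%):

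- *u* = 5%, *w* = 25%: 0.075/(0.075+0.855) = 8.1%.
- *u* = 5%, *w* = 50%: 0.05/(0.05+0.855) = 5.5%.
- *u* = *w* = 25%: 10.0%, no bias.
- *u* = 5%, *w* = 0: 0.10/(0.10+0.855) = 10.5%, a slight overstatement.

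**If few affected subjects stop** (*u* = 0, *w* = 10%):

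- *p* = 5%: 0.045/0.995 = 4.5%, with 30/0.995 − 30 = 0.15 expected exclusions and a 1−0.995^30 = 14% chance of any.
- *p* = 10%: 0.09/0.99 = 9.1%.

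**In counts.** Suppose that no completer reports a side effect, but two subjects stopped because of symptoms and were replaced. The plan reports 0/30 (exact 95% CI 0 to 11.6%). Counting everyone who started gives 2/32 = 6.3% (0.8 to 20.8%).

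**Against sampling error.** An observed 3/30 has an exact 95% CI of 2.1% to 26.5%, wider than any of the shifts above.

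**The case against.** The strongest objection is that the mechanism rests on a reading. Section 10 says when a participant's study is complete. It does not say that an unfinished battery counts as a withdrawal. With 17 tests in the Section 11 table, a subject who stops early but stays in the study could be treated as having missing tests and still be given the MSQ. This stands as a reason to define the term. It does not remove the problem, because a subject who leaves altogether because of symptoms is excluded on any reading.

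The second objection is about size. Vestibular testing takes 15 minutes (Section 9), risk is called minimal (Section 15), and the same goggles were used in at least two approved protocols (Section 21). Withdrawals may be few, and with *w* = 10% the shift is negligible at this sample size. That is fair. But safety is one of the questions SA1 asks, so an expectation of low risk cannot justify discarding the evidence that would test it. A confidence interval covers sampling error and does not reveal selective exclusion.

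Third, the protocol promises a safety and side-effect profile, not a numerical rate. The rate used here is the natural summary of that profile, and leaving out symptomatic stoppers distorts either one.

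Fourth, Section 12 limits stored data to vergence and vestibular results, so on a literal reading the MSQ answers of completers are not kept either. That is a separate matter and adds no weight here, though the fix has to touch Section 12.

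Finally, the consent form is not in the copy reviewed and may deal with data after withdrawal. That limits what can be said about the study as a whole, but the protocol text still needs to say it.

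**Conclusion.** The concern holds and should be fixed. Following Section 14 as written can remove symptom-driven stoppers from the SA1 safety result, and nothing in the plan would show that this had happened.

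The effect is conditional. Where affected subjects stop more often than others, side effects are understated. Where stopping is unrelated to symptoms, or nobody stops, there is no bias. If mainly unaffected subjects stop, the rate is slightly overstated. At an assumed true rate of 10%, with only affected subjects stopping, the reported figure would be 9.1%, 7.7% or 5.3% when a tenth, a quarter or half of them stop.

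The actual size cannot be known from the documents, and the shifts are smaller than the sampling uncertainty with 30 subjects. Confidence is medium because of the undefined term and the unknown rates. The SA2 and SA3 vergence values are not criticised on this ground.

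**What to change.** - **Section 14:** state what counts as withdrawal. For everyone who starts testing, keep the fact of stopping, the reason and any symptom responses for the safety analysis. If a subject asks for deletion, honour it but still count the withdrawal.
- **Section 11:** offer the MSQ at the point of stopping as well as after a full session.
- **Section 12:** add these items to the stored-data list.
- **Reporting:** give side effects with all starters as the denominator, and non-completion with reasons by group.
- **Unchanged:** replacement to 30 completers per group can continue for the vergence values.

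The cost is a few sentences and one extra questionnaire for each subject who stops early. No subjects are needed beyond the replacements already planned. The consent wording may have to be matched. The reported safety figure may look less favourable. If nobody withdraws, the results do not change.
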